7.3.2.4. Ascertainment and Confirmation of New-Onset AF Events

Screening for New-Onset AF: Within each RP's database, patients will be identified as having new-onset AF within 16 days after *Arexvy* vaccination if they had:

unpublished data on post-marketing adverse events reported to GSK through August 2024, which had a maximum time to onset of 8 days post-vaccination.

In one sensitivity analysis, our risk and control windows will be 1-28 days and 29-56 days respectively. This is based on: (i) the available evidence from literature on risk intervals for cardiac arrythmias after vaccination in older adults [Patone, 2022a; Patone, 2022b], and (ii) data from the Phase 3 efficacy trial which indicated that all new-onset serious AF events occurred within 28 days after vaccination (only serious reports are considered as they represent the events for which the participants were hospitalized due to their AF onset and only such reports would be captured in this study design) [GSK, 2023]. Further, using 28 days (versus, for example, 30 days) avoids potential day-of-week bias [Yih, 2016b]. In another sensitivity analysis, we will use risk and control windows of 1-3 days and 4-8 days respectively, since unpublished post-marketing reports have indicated a maximum time to onset of 3 days.

Of note, health care utilization is expected to vary by the day of the week, clustering on some days in the week compared to the others. Typically, vaccine safety studies account for potential day-of-the-week effects by using risk and control windows that are multiples of 7 [Yih, 2016b]. Our analyses with risk windows of 8 days and 3 days may be susceptible to day-of-the-week effects.

The date of the event will be the date of the first qualifying AF diagnosis if there are two outpatient codes. Continuous enrolment through Day 106 post-vaccination will be required for the primary AF inferential analysis, ensuring vaccinees have equal time to acquire a second diagnosis for AF in the outpatient/ED setting. The final analysis will include individuals who have AF and die during follow-up. We will also conduct a sensitivity analysis where continuous enrolment is required only through the control window (Day 16).

Arexvy vaccinees identified with AF via the claims-based algorithm will be assessed for a prior AF diagnosis code >365 days before the event date. The number of AF events meeting this criterion will be reported for each risk and control window combination.

Table 7 ICD-10-CM diagnosis codes for new-onset AF case-finding algorithm

Full Description	Code
Paroxysmal atrial fibrillation	148.0
Unspecified atrial fibrillation	148.91

Validation of New-Onset AF events: Materials for medical record review (including the abstraction and adjudication forms with case classifications and SOPs), will be developed prior to having results from the first monitoring query.

Since AF is a common health outcome among older adults, we will evaluate the PPV (95% CI) of our proposed algorithm for new-onset AF within a random sample of vaccinees who meet the algorithm. Our focus is on PPV because a sufficiently high PPV provides confidence that identified outcomes are true events.

As described in Section 7.3.2.1 above, we will identify a random sample of patients with new-onset AF across our RPs according to the algorithm developed in Table 4 and based on the number of charts needed in Table 3. If we obtain a PPV \geq 80%, it will provide reassurance that majority of new-onset AF events ascertained using the algorithm are true cases and reduce concerns regarding outcome misclassification; a claims data-only analysis will be conducted, possibly including adjustment for the PPV. If, contrary to expectation, the PPV of a coding algorithm is found to be below 80%, the inferential analyses will be restricted to chart-confirmed cases only. In this situation, additional charts will be sought to obtain 69 confirmed cases. This is based on an assumption of an IR between 10 and 50 per 1000 person-years and a RR of 2.

A trained abstractor will extract specific information from the hospital records onto a structured data abstraction form. The form will collect information from hospital admission notes, hospital discharge summaries, inpatient or outpatient cardiology consultation notes, inpatient or outpatient electrocardiograms (ECG), inpatient or outpatient Holter or event monitors, inpatient or outpatient telemetry strips, and inpatient or outpatient anti-arrhythmic medications administered. Forms will be reviewed by a clinician, preferably a cardiologist. To be considered a confirmed case of AF, there must be evidence of AF on one of the following studies: 1) ECG or rhythm strip, 2) Holter monitor, event monitor, or telemetry, or 3) pacemaker interrogation [Calkins, 2017]. Possible AF will be defined as a clearly noted AF diagnosis recorded by a clinician in the chart in the absence of any arrhythmia monitoring study. Abstractors and adjudicators will be blinded to vaccination date – i.e., they will not know whether the event occurred in the risk or control window.

If an algorithm for AF is validated within the data of a participating RP at the time of study conduct and meets our performance criteria, it will be considered whether to instead apply that algorithm and the protocol and SAP will be updated accordingly.

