		The primary analysis for the AF outcome will use risk and control windows of 1-8 days and 9-16 days, respectively (Figure 3 and Table 4). Sample size calculations were updated accordingly (Table 9). Sensitivity analyses have been added that will use risk and control windows of: a) 1-28 days and 29-56 days, respectively; and b) 1-3 days and 4-8 days, respectively.	2, 7	Due to the timing of various unpublished postmarketing reports of AF indicating a variable maximum time to onset of 8 days and 3 days.
		Vaccinees identified with AF via the claims-based algorithm will be assessed	7.3.2	There is interest in assessing whether a longer lookback period will

220149 (EPI-RSV-041 OA VS US DB) Protocol Amendment 2 Final

Amendment number	Date	Amendment or update	Section of study protocol	Reason
		for a prior AF diagnosis code >365 days before the AF event; the number of such individuals will now be reported descriptively.		identify prior AF history among those meeting the new-onset AF algorithm.
		The criteria used for confirmation of AF cases during medical record review were edited for clarity.	7.3.2	The original language was redundant.
		Additional covariates were added to describe vaccinees identified with GBS, ADEM, or AF via the claims-based algorithms.	7.3.3	There is interest in assessing whether other factors that may precipitate the outcomes of interest are documented in the individuals' claims history.
		Section 7.9 and Section 7.9.1 were revised with an updated plan of action in the event estimated sample sizes are not met at the planned end of study.	7.9, 7.9.1	Based on feedback received from the US FDA.
2	13 Jan 2025	New publications by Boos, 2020, Gundland, 2020, Parsons, 2020, and Tenembaum, 2007 were added to the Covariates, Section 7.3.3.	7.3.3	To align with SAP
		Study timeline and milestones were updated to reflect end of data collection by June 30, 2030, and final report delivery by December 31, 2031	2, 4, 7	Based on feedback received from the US FDA

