7.3.2.1. Medical record review of primary and secondary outcomes

At each annual monitoring query, for the evaluation of primary outcomes (i.e., GBS and ADEM), screening for potential events in the administrative claims data of the RPs will be done using the case-finding algorithms described in Table 4. Once each annual monitoring query is complete, given the rarity of GBS and ADEM, we will immediately seek to obtain the medical records of all patients identified as having possible events

based on our algorithms, abstract the data necessary to confirm these diagnoses from the medical records obtained, and implement a formal adjudication process with a team of expert clinicians, preferably neurologists, to confirm these events. Only confirmed cases will be included in the final primary analyses. For those outcomes, timing of symptom onset will be discerned from medical record review and timing of the event will be classified based on expert clinician adjudication (i.e., the date of diagnosis from the claims data will not be used due to concerns with misclassification).

Since AF is a more frequent health outcome in the population of interest compared to GBS and ADEM, a conventional approach will be followed to confirm the validity of the algorithms for each of these outcomes during the initial annual monitoring queries (we anticipate that the sample sizes for each AF validation can be accrued within the first or second annual monitoring periods given the prevalence of AF in the age group of the study population, but will need to assess initial monitoring query results) [Weinstein, 2023]. For the AF outcome, we *a priori* seek to identify an algorithm that has a positive predictive value (PPV) of \geq 80% to provide confidence that identified outcomes are true events. We estimate that 63 patients' charts (complete and adjudicated) would allow determination of the PPV of each case-finding algorithm with a maximum 95% CI of \pm 10%, assuming a PPV of 80% (Table 3).

The number of adjudicated charts needed for the AF validation will be determined based on the number of AF cases identified in the monitoring query(s). We expect to conduct the validation within 1-2 RPs, including the one RP with the most AF events identified during the initial monitoring queries.

Note that for analyses that include claims-based outcomes of interest in the inpatient setting, admission dates will be used, not discharge dates.

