7.7.3. Secondary analysis/Exploratory analysis

The analysis of new-onset AF, a secondary outcome, will be conducted using the same analytic approach as the primary outcomes described above in Section 7.7.2.1 in terms of the SCRI design as well as identification of fatal events. However, as explained in detail in Section 7.3.2.4, all claims-identified cases will be included for new-onset AF assuming the PPV for the diagnostic coding algorithm is $\geq 80\%$.

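### AF risk window of days 1-8 is set by time to onset but applied to the claims date, so late-coded cases fall into the adjoining control window and pull the IRR towards 1

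*Protocol*

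**What the plan says.** **Basis of the window.** Protocol section 7.3.2.4 supports the 8-day risk window with reports "which had a maximum time to onset of 8 days post-vaccination". Section 3 gives the same reason for the change: "Due to the timing of various unpublished postmarketing reports of AF indicating a variable maximum time to onset of 8 days and 3 days".

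**Windows.** Section 3 states: "The primary analysis for the AF outcome will use risk and control windows of 1-8 days and 9-16 days, respectively". Table 4 gives AF 0 extra days; GBS and ADEM have 7.

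**Event date for AF.** In section 7.3.2.4 the date is that of the first "qualifying AF diagnosis if there are two outpatient codes". For inpatient claims outcomes, section 7.3.2.1 says "admission dates will be used, not discharge dates".

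**Analysis set for AF.** Section 7.7.3: "all claims-identified cases will be included for new-onset AF assuming the PPV for the diagnostic coding algorithm is" at least 80%. Below 80%, section 7.3.2.4 restricts the analysis to chart-confirmed cases.

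**AF chart review.** For a confirmed case "there must be evidence of AF on one of the following studies" (ECG or rhythm strip, monitoring, pacemaker interrogation). No onset date is listed.

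**Contrast with GBS and ADEM.** Section 7.3.2.1 uses chart-adjudicated symptom onset, and "the date of diagnosis from the claims data will not be used due to concerns with misclassification". Section 7.9 admits possible misclassification of event timing, but its remedy covers only GBS and ADEM.

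**The concern.** The window is defined on one clock (onset) and the events are placed on another (first code or admission). Any delay between the two moves vaccine-caused cases later. Because day 9 is already control time, a case that slips past day 8 is usually not lost. It leaves the numerator and enters the comparison, so the IRR is reduced from both sides.

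For GBS and ADEM the protocol regards this risk as serious enough to reject the claims date, although those windows last 42 days. The AF windows last 8 days, so the same delay matters more.

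The bias is towards no effect, the unfavourable direction in a safety study. A PPV of at least 80% does not protect against it, because PPV tests whether AF is real and not when it began.

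**Working it through.** **1. The plan's own figure.** Table 9 gives 69 cases at RR 2 with 80% power, two-sided alpha 0.05 and equal windows. The cited self-controlled case series formula, with r = 0.5, is n = (z₀.₉₇₅ + z₀.₈₀√B)²/A. At RR 2, A = 0.1133 and B = 0.9426, so n = (1.960 + 0.842 × 0.971)²/0.1133 = 68.09, rounded up to 69. Control cases: 69/3 = 23. Vaccinees at 1 per 1000 person-years: 23 × 365.25/(8 × 0.001) = 1,050,094. All agree with Table 9. The calculation assumes no timing error.

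**2. Effect of delay.** Let a and b be the shares of the excess (vaccine-caused) cases dated on days 1-8 and days 9-16. Background is taken as flat, so delay leaves its split unchanged. At true RR 2 the expected IRR is (1 + a)/(1 + b).

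**3. Assumed lag (not in the protocol).** The lag in whole days is an exponential lag of mean m rounded down: P(lag = k) = (1 − q)qᵏ, with q = exp(−1/m). A share w of cases is delayed; the rest have zero lag. Power is for an exact two-sided binomial test with 69 cases, which needs at least 44 in the risk window; the probability per case is IRR/(1 + IRR).

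| Onset of excess cases | Delay | a | b | Expected IRR | Exact power, 69 cases |
|---|---|---|---|---|---|
| Days 1-8 | none | 1.000 | 0.000 | 2.00 | 74% |
| Days 1-8 | 30%, mean 2 days | 0.943 | 0.056 | 1.84 | 62% |
| Days 1-8 | 30%, mean 5 days | 0.865 | 0.108 | 1.68 | 48% |
| Days 1-8 | half, mean 5 days | 0.775 | 0.180 | 1.50 | 31% |
| Days 1-8 | all, mean 5 days | 0.549 | 0.360 | 1.14 | 5% |
| Days 1-3 | half, mean 5 days | 0.875 | 0.100 | 1.71 | 50% |
| Days 1-3 | all, mean 5 days | 0.750 | 0.199 | 1.46 | 27% |

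Example, half delayed: (1 + 0.775)/(1 + 0.180) = 1.50. The days 1-3 rows keep the same total excess but place onset earlier.

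Rounding the lag down is the milder choice. A continuous exponential lag in all cases gives 1.41 instead of 1.53 at mean 2 days, and 1.07 instead of 1.14 at mean 5 days.

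**4. Baseline for power.** The exact test has 74% power at RR 2 with 69 cases; the cited formula gives 80.5%. This is a difference of method and not an error in the plan. The fair comparison is 74% with 31%.

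**5. More cases.** At 1,000 cases the exact test has over 99% power for an IRR of 1.34 or more, and 53% at 1.14. The expected IRR does not change.

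**6. Sensitivity analysis (a), days 1-28 against 29-56.** Nearly all late-coded cases stay in the risk window, but an 8-day doubling is spread over 28 days: 1 + 8/28 = 1.29. The cohort that yields 69 cases in the primary windows yields 23 × 28/8 = 80.5 control cases and about 184 in total. Power by the cited formula is about 40%.

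**7. A gapped control window, days 17-24.** In the half-delayed scenario 3.6% of the excess is dated on days 17-24. The expected IRR is (1 + 0.775)/(1 + 0.036) = 1.71, instead of 1.50.

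**The case against.** - **The lag may be short.** Section 7.3.2.4 says, when explaining sensitivity analysis (a), that only hospitalised AF would be captured, and admission may follow onset closely. But the same section dates cases with two outpatient codes, and enrolment to Day 106 exists for them. The plan cannot rely on hospital-only capture. A short lag remains possible, and the attenuation would then be small.
- **Onset may be early.** Eight days is the maximum reported, and other reports had a maximum of 3 days. This stands, and is why the days 1-3 rows are shown.
- **Onset is not defined.** The reports are unpublished and the start of the rationale sentence is not visible. If onset there meant first diagnosis, the mismatch shrinks. The amendment table does state the onset basis separately.
- **Case numbers may be large.** With PPV of at least 80% all claims cases enter, and Table 3 considers 1,000 to 100,000 identified cases. This stands for power. However, section 7.7 triggers the final analysis once the required events have accrued, so a count near 69 cannot be excluded, and numbers do not remove bias.
- **A wider window is planned.** Sensitivity analysis (a) does guard against late coding, but it dilutes the effect to about 1.29 and is not the primary AF analysis. Sensitivity analysis (b), days 1-3 against 4-8, has the same weakness in narrower windows.
- **Chart-confirmed branch.** A reader might infer that chart-confirmed AF will also be placed by claims date. The protocol does not say so. It does not say which date applies, and the abstraction forms are still to be developed.

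**Conclusion.** The point holds as a bias towards 1 in the primary AF analysis. The onset-based window, the claims-based date and the adjoining control window are all in the text, and the stated timing remedy leaves AF out.

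The size is a range, because the lag is an assumption. At true RR 2 it runs from slight attenuation (1.84) to near loss of the signal (1.14) with onset spread over days 1-8, and is milder if onset is confined to days 1-3.

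A reader might conclude that the plan would hide a doubling of AF risk. The protocol does not support that. It gives no lag, large case numbers would still detect moderate attenuation, and the 28-day sensitivity analysis is a partial guard. The supported statement is that the estimate is attenuated and that, near 69 cases, power may be well below plan.

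This should be fixed. AF is a secondary outcome, so the point does not affect the primary objectives.

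**What to change.** 1. **Record onset.** Add to the AF abstraction form the date of first AF symptoms or, if there were none, of first rhythm documentation, adjudicated blind to vaccination date. If the PPV is below 80%, assign chart-confirmed cases to windows by that date, and say so in section 7.3.2.4.
2. **Prespecify a gapped analysis for the claims-based branch.** Fix it now, before any IRR is computed: risk days 1-8 and an equal-length control window after a fixed gap, for example days 17-24. Report the onset-to-code lag from the validation charts to help interpret the primary IRR. Do not reset the primary window from that lag: the 95th percentile of about 63 charts rests on roughly 3 observations (5% of 63), from 1-2 research partners.
3. **State the limitation.** Say in section 7.9 that the AF analysis dated by diagnosis is biased towards the null.

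**Cost.** One field on charts already being abstracted, and protocol wording. For the gapped analysis, the protocol's own rule (Day 16 + 90 = Day 106) would extend enrolment to Day 24 + 90 = Day 114, losing some members who disenrol. The gap reduces the bias without removing it. Where there were no symptoms, first rhythm documentation may coincide with the first coded visit, so the recorded date will not recover every delay.

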*In the primary analyses, cases with symptom onset (established from chart review) in the control window may present with coded diagnoses (identified in claims data) up to 7 days after the end of the control window ('extra days'). Date of symptom onset is deemed as the date of chart confirmed events. Only events with dates of symptom onset in risk and control windows contribute to the primary analyses.

**Post-index enrolment requirement does not enforce survival through the end of all evaluation windows postvaccination. Vaccinated cases with evidence of death in the post-index window will contribute to the analyses.

Figure 2 Illustration of SCRI design for new-onset AF¹ (example with 1 inpatient diagnosis code)

Vaccine (day 0)		
Baseline (day –365, -1)			
Study selection criteria; participant characterization		*	
	Risk window (day 1,8)	Control window (day 9,16)	
Pre-index enrollment (gaps up to 45 days allowed)	Post-index e (no gaps all	enrollment* owed)	
· · · · · · · · · · · · · · · · · · ·		r N	

†Analyses will be claims-based if estimated PPV from descriptive monitoring queries is ≥80% and chart- confirmed if PPV <80%.

*Post-index enrolment requirement does not enforce survival through the end of all evaluation windows postvaccination. Vaccinated cases with evidence of death in the post-index window will contribute to the analyses.

Figure 3 Illustration of SCRI design for new-onset AF^I (example with 2 outpatient or ED diagnosis codes) ^{II}

†Analyses will be claims-based if estimated PPV from descriptive monitoring queries is ≥80% and chart- confirmed if PPV <80%.

* Post-index enrolment requirement does not enforce survival through the end of all evaluation windows postvaccination. Vaccinated cases with evidence of death in the post-index window will contribute to the analyses. Abbreviations: AF: atrial fibrillation; ED: emergency department; PPV: positive predictive value.

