Number of AF cases identified	1 000	5 000	10 000	20 000	100 000		
Actual PPV	Number	Number of adjudicated charts needed					
60%	86	92	93	93	94		
65%	82	87	88	89	89		
70%	76	81	82	82	82		
75%	69	72	73	73	73		
80%	59	62	63	63	63		
85%	48	50	50	50	50		
90%	35	36	36	36	36		

Table 3Number of charts needed to obtain a 95% two-sided Cl ±10% for
new-onset AF validation*

Abbreviations: AF: atrial fibrillation CI: confidence interval; PPV: positive predictive value.

*The needed sample size for a 2-sided 95% CI for a binomial proportion with a 10% margin of error was calculated using a range of possible AF cases. These calculations were done in Excel.

To account for the fact that approximately 30%, or more, of hospital medical records might not be available to review, we will oversample from a random sample of the total AF cases identified according to the case-finding algorithm to ensure we obtain the target number of charts needed. Once the initial annual monitoring query, which will include new-onset AF, is complete, medical records of patients in the sample will be requested immediately. Once charts have returned, the data necessary to confirm these diagnoses from the medical records will be abstracted, implement a formal adjudication using a team of expert clinicians, preferably cardiologists, to confirm these events, and determine the PPV of the algorithm for new-onset AF.

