7.5. Study size

The sample size and power calculations are estimated for the primary outcomes of the study, GBS and ADEM, and the primary risk (days 1-42) and control (days 43-84) windows. In the US, background rates of GBS reported in the literature range from 1.6 to 6.3 per 100 000 person-years in the overall population. In those ≥ 60 years of age, the IRs vary from 2.4 to 4.7 per 100 000 person-years in studies conducted over several years between 1935 and 1987 [Law, 2021]. More recent publications are reporting IR ≥ 4 GBS cases per 100.000 person-years in older adults. A study conducted in the US on background rates of adverse events of special interest reported a GBS IR of 4.6 per 100.000 person-years in adults ≥ 65 years of age [Moll, 2023]. The background rate in the analysis conducted by [Lloyd, 2024] was 4.4 per 100,000 person-years (unpublished). Background rates of ADEM range from 0.3 to 0.6 per 100 000 person-years in the overall population [Pohl, 2016].

The estimated number of vaccinated individuals needed to detect an association between *Arexvy* and the outcomes, assuming 80% statistical power, a two-sided alpha = 0.05, and an equal duration of 42 days for the risk window and 42 days for the control window, are

reported in Table 8 for GBS and ADEM for a range of RRs to be detected and a range of IR for the outcomes. Table 9 is for AF and is based on risk and control windows of 8 days.

Using a background rate for GBS of 4.5 cases per 100 000 person-years (taken as the average from [Lloyd, 2024] (4.4) and Moll, 2023 (4.6)), a total number of 69 cases in the combined risk and control intervals provides 80% power to reject the null hypothesis of no association when the true RR is \geq 2.0. Approximately 4.4 million vaccinated patients are needed to accrue the number of cases of GBS (Table 8).

Using a background rate for ADEM cases of 0.45 per 100 000 person-years, a total number of 12 cases in the combined risk and control intervals provides 80% power to reject the null hypothesis of no association when the true RR is \geq 7.0. Approximately 3.9 million vaccinated patients are needed to accrue the number of cases of ADEM (Table 8).

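### The AF validation yields one PPV pooled over the risk and control windows, and scaling both windows by it would leave the AF rate ratio unchanged

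*Protocol*

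**What the plan says.** Section 7.3.2.4 defines the events to be found: "patients will be identified as having new-onset AF within 16 days after" vaccination. That span covers both the risk window (days 1-8) and the control window (days 9-16). The PPV is to be evaluated "within a random sample of vaccinees who meet the algorithm". Section 7.3.2.1 describes the draw in similar terms, to allow for unobtainable charts: "we will oversample from a random sample of the total AF cases identified according to the case-finding algorithm". Its purpose is to "determine the PPV of the algorithm for new-onset AF". About 63 charts are planned, sized for one proportion with a margin of ±10 points at a PPV of 80% (Table 3).

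That single estimate decides the analysis. The footnotes to Figures 2 and 3 state: "Analyses will be claims-based if estimated PPV from descriptive monitoring queries is ≥80" percent, with chart-confirmed cases used otherwise. For the claims-based branch, Section 7.3.2.4 adds that "a claims data-only analysis will be conducted, possibly including adjustment for the PPV". Section 7.9 says quantitative bias analyses of outcome misclassification may be done. None of these places, nor Sections 7.7.2.3 or 7.7.3, splits the sample, the estimate or the 80% rule by window.

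**The concern.** The AF result is a ratio of event counts in two windows of equal length. What misclassification does to that ratio depends on how the PPV in the risk window compares with the PPV in the control window; the average level alone does not settle it. The validation is set up to deliver only the average.

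Two things follow. First, the simplest reading of an adjustment for the PPV, multiplying the counts by it, has no effect on the ratio. Second, when the vaccine has a real effect and false positives arrive at a steady rate, the extra true cases raise the PPV in the risk window, so the control-window PPV lies below the pooled value. The observed ratio is then pulled toward 1, the unfavourable direction in a safety study. False positives are not remote: Table 4 cites published PPVs of 67.5% to 75.7% for ICD-10-CM AF algorithms.

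**Working it through.** **Inputs.** From the protocol: 8-day risk and 8-day control windows (Section 7.5: "Table 9 is for AF and is based on risk and control windows of 8 days"), target RR 2 and 69 cases, 23 of them in the control period (Table 9), about 63 charts (Table 4) and the 80% rule. Assumption, because the protocol gives no PPV by window: the same number of false positives in each window.

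**Reproducing the plan's figures.**
- Charts: n0 = 1.96² × p(1 − p) / 0.10², then n = n0 / (1 + (n0 − 1)/N). At p = 0.80 this gives 58, 61, 62, 62 and 62 for N = 1,000 to 100,000, against 59, 62, 63, 63 and 63 in Table 3: agreement within one chart.
- Cases: the signed-root likelihood-ratio formula of the cited sample-size method, with half the time at risk, two-sided alpha 0.05 and 80% power, gives 68.1, rounded up to 69 at RR 2. It matches every row of Tables 8 and 9.

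**Scaling by one PPV.** With 46 risk-window and 23 control-window cases, (46 × PPV)/(23 × PPV) = 2.00 whether PPV is 0.70, 0.80 or 0.90.

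**What a pooled 80% can contain.** Take 100 claims events, true RR 2, pooled PPV 80%:
- true events: 80 × 2/3 = 53.3 risk, 80 × 1/3 = 26.7 control
- false positives: 10 and 10
- risk-window PPV = 53.3/63.3 = 84.2%
- control-window PPV = 26.7/36.7 = 72.7%
- observed IRR = 63.3/36.7 = 1.73, and still 1.73 after multiplying both counts by 0.80.

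**Two corrections that do not cancel.**
- (a) Window-specific: IRR × PPV_risk/PPV_control = 1.727 × 0.842/0.727 = 2.0.
- (b) Subtraction: (63.3 − 10)/(36.7 − 10) = 2.0, using only the pooled PPV and the equal-false-positive assumption.

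**Range under the same assumption.**

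| True RR | Pooled PPV | Risk PPV | Control PPV | Observed IRR |
|---|---|---|---|---|
| 1.5 | 80.6% | 83.3% | 76.9% | 1.39 |
| 2 | 80.0% | 84.2% | 72.7% | 1.73 |
| 2 | 83.3% | 87.0% | 76.9% | 1.77 |
| 2 | 90.0% | 92.3% | 85.7% | 1.86 |
| 3 | 80.0% | 85.7% | 66.7% | 2.33 |

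At RR 1 the two window PPVs are equal and the observed IRR is 1.

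**Precision of a window-specific correction.** With 32 charts in a window and PPV 80%, the half-width is 1.96 × √(0.8 × 0.2/32) = 0.139, about ±14 points. For a 32/31 split at PPVs of 84.2% and 72.7%:
- factor = 0.842/0.727 = 1.16
- SE of its log = √(0.158/(32 × 0.842) + 0.273/(31 × 0.727)) = 0.134
- 95% CI = 1.16 × exp(±0.263), about 0.89 to 1.51
- corrected IRR, validation error alone: about 1.54 to 2.60.

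An unstratified draw of 63 would fall about 40/23, and the same formula gives about 0.87 to 1.54. For correction (b), moving the pooled PPV by ±10 points gives (63.3 − 15)/(36.7 − 15) = 2.23 and (63.3 − 5)/(36.7 − 5) = 1.84.

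**The case against.** The strongest reply is that the protocol never says the adjustment would be a simple multiplication. It is optional, its form is open, and the SAP, which is not shown, may define it. A reader might infer that a PPV adjustment is planned and that a pooled PPV cannot correct the IRR. The text supports neither: it says only that an adjustment is possible, and correction (b) recovers 2.0 from the pooled PPV alone if false positives are equal. That part of the objection stands. What remains is that the pooled figure cannot test whether false positives are equal.

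It can also be said that a simple random sample already contains both windows, so PPV by window can be tabulated without stratifying, and that balancing the draw barely improves precision. Both are right. The gap lies mainly in what is sized and reported.

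A reader might further suppose that more ECG testing soon after vaccination would create a PPV difference. The protocol reports no such pattern. Under Section 7.3.2.4, AF seen on an ECG is a confirmed case, so extra testing would find true AF. That is detection bias, which a PPV by window would not reveal.

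Finally, AF is a secondary outcome, Section 7.9 openly lists misclassification as a limitation, and the stated purpose of the 80% rule is confidence that identified events are real, which a pooled PPV serves. These points limit the weight of the concern without removing it.

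**Conclusion.** The point holds in a limited form. As written, the plan can pass the 80% rule, leave a real AF effect attenuated, apply an adjustment that does nothing if it takes the multiplicative form, and never check whether misclassification differs between windows. The size is moderate: at RR 2, an observed IRR of about 1.73 at the 80% threshold and 1.86 at a pooled PPV of 90%. These figures rest on equal false positives per window, which the protocol neither states nor contradicts. With exactly 69 claims events and an observed IRR of 1.73, power would be about 61%, and 108 events would be needed for 80%. Claims-identified AF will probably exceed 69 events, so attenuation matters more than lost power.

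**What to change.** From the same total number of charts, report PPV with its CI separately for claims days 1-8 and 9-16. Preferably the coordinating center balances the draw by claims window before charts are requested; Section 7.7.1 already has outcomes counted by window, and abstractors and adjudicators stay blinded. Recover the pooled PPV for the existing 80% rule by weighting each window's PPV by its share of claims events. If charts have already been drawn at random, tabulate those by window.

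Keep the unadjusted claims IRR as the main result in that branch. In place of the open-ended adjustment, prespecify a sensitivity analysis with both (a) IRR × PPV_risk/PPV_control, with PPV sampling error carried into the CI, and (b) subtraction of equal false positives per window based on the pooled PPV.

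The cost is one tabulation and one added analysis. The downside is precision: (a) will be imprecise at about 32 charts per window and should be read only as a sensitivity analysis. A margin of ±10 points in each window would take about 125 charts.
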